No-shows are defined as scheduled appointments that are neither attended nor canceled, and represent a "missed opportunity" on several levels. First, for patients, no-shows may contribute to reduced access and increased wait time. A VA Office of Inspector General audit noted that "reducing unused outpatient appointments could improve timeliness of Veterans' patient care"⁷. Another report found that inefficiencies caused by no-shows in VHA make it "difficult to meet the performance measure of seeing new patients within 30 days"⁴⁰. Second, no-shows contribute to inefficient use of healthcare resources. No-shows result in appointment slots that unexpectedly go unused; further, after a no-show, clinics frequently spend time re-scheduling. The same Office of Inspector General audit estimated that suggested that reducing no-shows in could allow VHA facilities to more efficiently use millions of dollars each year⁷. Third, no-shows represent a missed clinical opportunity. The appointment was scheduled for a clinical reason, which does not get addressed when there is a no-show. Many vulnerable, at-risk groups, including psychiatric patients, ethnic minorities, and low-income patients are disproportionately impacted by no-shows^{4,41,42}, which can contribute to further disparities in clinical outcomes and quality of care^{4,41}.

Why are current approaches to address no-shows in VHA inadequate?

VHA struggles with elevated no show-rates, which have not improved in recent years. VHA's overall no-show rate continues to be approximately 13-14%, far above Secretary Shulkin's stated goal of five percent. In FY2015 this rate led to a total of over nine million no-shows. Despite VHA efforts aimed at reducing no-shows, such as recall scheduling and new patient orientation clinics, no-show rates have been static for years, according to VHA Support Service Center (VSSC) data (see **Figure 1**)¹⁵.

Figure 1. National VA No-Show Rates Between 2013 and 2016

What Veterans are likely to no-show and why?

Research led by our operational partner [name] has described some common characteristics of Veterans who miss visits: mental health and rehabilitation are the service lines with the highest no-show rates; no-show rate increases with age of the appointment (i.e., how long ago it was scheduled); new patients have higher no-show rates; male Veterans have somewhat higher no-show rates than females until age 65, after which it equalizes².

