Effectiveness of enhanced appointment reminders in varying clinical and patient populations: Although not all studies have been consistent, empirical data often suggest that the largest impacts on reducing no-show rates with appointment reminders have been in mental health^{11,44,47,60}. This may result in part from higher baseline no-show rates in mental health compared to other specialties. Having more room for improvement may be important for success of BE interventions trying to improve patient adherence⁶¹. Primary care is also a vital setting to conduct this research. First, treatment access in primary care is a VHA high priority. Second, the risk for missed appointments may be rising in primary care⁶². Because many VHA primary care clinics are shifting to patient-centered scheduling (from recall scheduling), more appointments are being scheduled months in advance (i.e., at the time of the last appointment), a well-known risk factor for no-shows². Reminders may be especially vital for new patients: they are known to have higher no-show rates than established patients², may be unfamiliar with clinic procedures, and especially responsive to appointment-related messages⁶³.

SIGNIFICANCE AND INNOVATIONS

This proposal directly tackles the priority areas of access and mental and behavioral health. In personal discussion with [name], Senior Medical Advisor to the

Office of Veterans' Access to Care, [name], has described reducing no-shows as "critical to efforts to improve access," a belief supported by empirical data linking no-shows to access and wait time^{7,40}. We use mental health clinics as one of the treatment settings in this proposal because of their elevated no-show rates^{6,10,43} and because mental health appointments are typically allocated more time, with therefore fewer available slots.

Applying insights from BE to enhance appointment attendance is innovative. With the exception of a few studies in the U.K.'s National Health Service^{21,31}, BE has not been incorporated and evaluated in the design and content of appointment reminders. Nonetheless, BE has a robust scientific grounding, with a broad array of successful applications in contexts ranging from financial planning to consumer energy use to healthcare^{19,27,64,65}.

This proposal is closely aligned with VHA operational partners and their priorities. Our partnerships include the:

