Our primary outcome will be no-show rate, or the proportion of total appointments that are classified as a no-show, relative to the total number of appointments scheduled. The numerator (“no-shows”) consists of appointments marked as a no-show and appointments canceled by the patient or clinic after the appointment time. The denominator (“total appointments”) consists of no-shows and completed appointments. No-show rates will be measured at the provider-level.

Table 3. Trial Outcomes (Aims 2 & 3)

Outcome	Measure	Data Source
Primary	No-show rate	CDW
Secondary	Cancellation rate	CDW
	Advance cancellation rate	CDW
	Patient-initiated cancellation rate	CDW
Exploratory	Raw wait time	CDW
	Clinically indicated wait time	CDW
	Waiting room time	SHEP
	New mental health appointment wait time	CDW

Our secondary outcome will be cancellation rate, defined as the proportion of scheduled appointments that are marked as canceled. In addition to overall cancellation rate, we will also determine the rate amongst the subset of cancellations that are advance cancellations and patient-initiated cancellations. Advance cancellations, defined here as at least five days before appointment, provide a metric with a reasonable window of time (informed by preliminary data provided by our schedulers) that allows the opportunity to fill a cancelled slot with another waiting Veteran. Patient-initiated cancellations provide a more specific indication of intervention effects on cancellation behavior. Cancellation rates will be measured at the provider-level.

Finally, as exploratory outcomes, we will calculate wait time and number of unique patients seen per day. The latter is simply the number of daily completed encounters, adjusting for patients who have multiple encounters in the same day. For wait time, we will use multiple validated metrics:

- Raw wait time is defined as the length of time in days between the date an appointment was created and the date the appointment was completed⁷⁴. If an appointment is cancelled or a no-show, the wait time will be calculated based on the next appointment that is scheduled and completed in the same clinic stop code.

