These no-show, cancellation, and wait time metrics are consistent with ones used by our operational partners and VSSC. To construct these standardized measures, we will extract administrative data in CDW on appointment/encounter variables, including date, location, provider, stop code, and cancellation remarks. Wait time measures will be stratified based on new vs. established patients. “New patients” are those who have not completed another appointment in a given specialty and parent VA facility during the prior 24 months.

Baseline characteristics (Aims 2 and 3): To demonstrate balance among study arms, we will extract information from CDW on subject demographics (age, sex, race/ethnicity, service connection status, and rurality), diagnoses (proportion with common chronic conditions: depression, PTSD, diabetes, and hypertension), and appointment features (clinic type, new vs. follow-up, provider, and time between appointment creation and actual appointment). We will use protocols and code for data extraction previously established by Drs. [name] and [name] for these variables.

Qualitative assessment (Aim 4): The primary goals of our semi-structured interviews are to identify features of our interventions that act as facilitators or barriers to widespread implementation, and to suggest potential modifications or adaptations to the interventions that would promote larger-scale implementation, long-term maintenance, and adaptability to other reminder modalities. We will develop and pre-test interview guides for VHA staff and Veterans.

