Aims 2 and 3: We will first conduct univariate analyses to describe the “Table 1” baseline demographic, diagnostic, and appointment utilization characteristics of subjects and clinics in the usual care and intervention conditions. Then we will tabulate the total number of no-shows and total number of unique subjects with at least one no-show during the study period. For subjects with no-show(s), we will calculate the proportion with a single vs. multiple no-shows, and the mean and median number of no-shows. To analyze our primary outcome, no-show rate, we will use standard mixed effects correlated logistic regression since the outcome is binary at the individual-level. (We will use a similar approach to analyze intervention effects on our secondary outcomes, cancellation rates.) These will model the odds of no-shows as $\log[\text{odds}(p_{ij})] = b_i + \beta_0 + \beta_1 * \text{trt}(1)_{ij} + \beta_2 * \text{trt}(2)_{ij} + \beta_3 * \text{trt}(3)_{ij} + \beta_4 * \text{trt}(4)_{ij} + \text{location}_{ij}$, where p_{ij} is the no-show probability for provider i in location j , $\text{trt}(k)$ are indicators for the 4 interventions, and location_{ij} corresponds to the location for provider i . The random effect, b_i , is assumed to be normal with mean 0 and constant variance (σ^2_b) and will be used to account for repeated measures correlation for the individual subject outcomes for each provider; the model parameters, ($\beta_1, \beta_2, \beta_3, \beta_4$), represent log odds ratios of no-shows comparing the four intervention groups to the control group. They will be estimated using maximum likelihood estimation and will be used to test the hypotheses of Aim 1. This mixed model is a longitudinal model and can accommodate some forms of missing data, provided the missingness mechanism is non-informative. We can also estimate absolute risk differences between the interventions and usual care. No-show rates will also be presented in several ways: overall rate (i.e., for all study participants in each of the five study arms), stratified by specialty (mental health vs. primary care), stratified by patient type (new vs. follow-up), and over multiple follow-up periods (six and 12 months to determine duration and decay over time of any effect). We will also conduct exploratory subgroup analyses, which may identify particular patient populations where

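### New-patient status changes with visits completed during the trial, so the new-versus-follow-up results depend on earlier outcomes and can be biased in either direction

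*Combined protocol and SAP*

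**What the plan says.** The only definition of the term is in section I (Measures): new patients "are those who have not completed another appointment in a given specialty and parent VA facility during the prior 24 months". It follows directly on the statement "Wait time measures will be stratified based on new vs. established patients". No date is given from which the 24 months run back, and no rule covers a visit rebooked after a no-show.

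Three uses matter:
- Wait-time results, to which section I attaches the definition.
- No-show rates, which section J will show "stratified by patient type (new vs. follow-up"), with no definition of its own.
- The baseline table in section I, which lists new versus follow-up as an appointment feature among the variables meant to show balance between arms.

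The no-show denominator "consists of no-shows and completed appointments", so one Veteran can contribute several appointments. Section H extends the intervention to the letters sent after a no-show. The Background says of new patients that "they are known to have higher no-show rates than established patients", and that they may be "especially responsive to appointment-related messages".

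**The concern.** A subgroup label should be settled before the outcome it is used to stratify. Here a completed visit removes a Veteran from the new stratum and a no-show keeps the Veteran in it. From the second trial appointment on, membership depends on that Veteran's earlier results on the primary endpoint, and those results may differ by arm. A letter that works moves more Veterans into follow-up, so the two strata no longer hold comparable Veterans across arms.

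At stake is the reading of the new-versus-follow-up contrast. The Background raises the possibility that new patients respond more. The labelling rule alone can produce such a pattern, or hide one. A baseline table built on the same rule would also partly describe what happened after randomisation.

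**Working it through.** The plan gives no figure for this stratum, so there is nothing to reproduce. The check asks what the rule does to a known effect.

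**Inputs from the protocol.** The definition and the denominator are as quoted. For VHA as a whole, the "overall no-show rate continues to be approximately 13-14" per cent. New patients have a higher rate, of unstated size. Section K uses effects of 1.9 and 2.7 points.

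**Assumed inputs.** New-patient no-show risk averages 20% and varies between Veterans as a Beta distribution with within-Veteran correlation 0.2. The letter multiplies everyone's odds of a no-show by 0.8. Every no-show is rebooked in the same arm, up to 3 attempts. The protocol gives none of these values.

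**Formula.** A Veteran with risk p reaches attempt k+1 while still new with probability p^k, and no-shows there with probability p^(k+1). The stratum rate is the sum of E[p^(k+1)] divided by the sum of E[p^k], for k = 0, 1, 2. The unbiased comparison is E[p] at the first visit.

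**Control.** The Beta parameters sum to 1/0.2 − 1 = 4, giving 0.8 and 3.2. The moments are 0.2000, 0.0720 and 0.0336. Rate = 0.3056 / 1.2720 = 24.03%, against 20.00% at the first visit.

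**Treated.** Each p becomes 0.8p / (1 − p + 0.8p). The moments, by numerical integration, are 0.1727, 0.0564 and 0.0245. Rate = 0.2536 / 1.2291 = 20.63%, against 17.27% at the first visit.

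**Effect.** First visit: 20.00 − 17.27 = 2.73 points. Stratum as defined: 3.39 points before rounding. Factor: 3.39 / 2.73 = 1.24.

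**Relative scale.** The odds ratio is 0.835 at the first visit and 0.822 in the stratum. The risk ratio is 0.864 and 0.859. The distortion lies mainly in the absolute difference.

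**Both strata together.** Give each Veteran who starts as new four appointments, under the same assumptions. The changing label gives 3.57 points in new and 2.21 in follow-up. A fixed label gives 2.73. The rule alone creates a gap of 3.57 − 2.21 = 1.36 points when every Veteran has the same odds ratio.

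**When there is no bias.** If all Veterans share one risk p, the stratum rate is p(1 + p + p²) / (1 + p + p²) = p, so repeat counting alone does nothing. With no true effect, both arms rise equally and the difference is 0.00.

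**When it reverses.** Assume 11% of Veterans have 50% risk and do not respond, while 89% have 8% risk and fall to 8 − 2.70/0.89 = 4.97%. The first-visit effect is 2.70 points. With every no-show rebooked, up to 8 appointments:
- Control: 0.1870 no-shows / 1.1865 appointments = 15.76%.
- Treated: 0.1561 / 1.1557 = 13.51%.
- Difference: 2.25 points, factor 0.83. With rebooking probabilities of 0.6 and 0.3 it is 2.49 and 2.61.

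**Range over assumptions, common odds ratio.**
- Odds ratio 0.8, risk 15–25%, correlation 0.1–0.3, 2–6 attempts: factor 1.06 to 1.67.
- The 20%, 3-attempt case with correlation 0.05: factor 1.07.
- Base rate 13.5%, first-visit effect 2.7 points, correlation 0.05–0.30, rebooking probability 0.3–1.0: factor 1.02 to 1.79. A common risk ratio instead gives up to 2.39.

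**The case against.** The strongest reply is that the protocol never says the 24 months roll with each appointment. Section J speaks of patient type, and section I lists the item under baseline characteristics, which fits a status fixed at entry. The definition sits with the wait-time measures, so its use for no-show rates is an inference. This stands as a caution. But section I also calls the item an appointment feature, no other definition is given, and nothing freezes the status. If a fixed label was intended, one sentence would settle it.

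A reader might go further and infer that the plan stratifies on the primary outcome itself. It does not. The definition refers to another appointment, so an appointment's own result never sets its stratum, and each Veteran's first trial appointment is classified on prior history alone.

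The reach is also limited. Section J's primary model has treatment and location terms and a provider random effect that "will be used to account for repeated measures correlation for the individual subject outcomes for each provider". Patient type is not in it. No hypothesis compares new with follow-up patients, and wait time is exploratory. Aim 4 draws on post-hoc subgroups only if the intervention proves ineffective, and with no true effect this bias is zero. All of that stands.

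Lastly, an appointment-level label answers a fair operational question and matches the metrics that the operational partners use. That is a reason to show it alongside, not to rest a subgroup effect on it.

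**Conclusion.** The concern holds in a limited form. On the natural reading of section I, new-versus-follow-up membership after the first trial appointment depends on earlier post-randomisation outcomes. The stratified effects, chiefly absolute differences, can be biased. The primary comparison is not affected by this rule.

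It would be tempting to conclude that the rule overstates the effect in new patients. The documents do not support that. Overstatement needs Veterans to differ in risk and the effect to reach those at higher risk. The first is plausible, since section J itself separates single from multiple no-shows, but the protocol gives no within-Veteran correlation, rebooking rate or effect by risk level. Under the assumptions shown, 2.7 points can appear as 3.4, or 2.70 as 2.25, or be left unchanged. Neither sign nor size can be fixed from the protocol. The effect on wait-time strata follows by the same reasoning and was not quantified.

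**What to change.** In sections I and J, state that each Veteran is classified once per specialty as new or established, using completed visits in the 24 months before that Veteran's first eligible appointment in the intervention period. Use this fixed label for the stratified no-show and wait-time results and for the baseline table. Also report results for the first new appointment alone. Even with a fixed label, the number of appointments a Veteran contributes can depend on earlier no-shows, and the first-appointment result is free of that as well.

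The cost is a sentence in each section and a change in the order of derivation in the data code. Section B already allows extraction of up to two years of data before study start, which supplies the history if the full two years are taken. There is a small downside: the fixed label departs from the rolling operational definition and, for Veterans who start as new, mixes first and later visits. The rolling version can be shown beside it as descriptive.

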Aim 1: Develop and iteratively refine BE-informed messages based on Veterans' perceptions, and incorporate them into enhanced appointment reminders.

Hypothesis: Perceptions of messages will be consistent with our conceptual framework and not associated with emotional harms.

Aim 2: Determine the effect of four versions of enhanced appointment reminders on measures relevant to treatment access, compared with usual reminders.

Hypotheses: 1. Each intervention group will have a lower no-show rate, as compared with usual care. 2. Each intervention group will have a higher advanced cancellation rate, as compared with usual care. Exploratory

Hypothesis: Wait time will be shorter in intervention groups than with usual care.

Aim 3: Evaluate differences in treatment effect associated with four versions of enhanced appointment reminders.

Hypothesis: Effect size of nudges will vary by intervention arm such that some types of nudges will have a larger proportional effect than others.

Aim 4: Characterize potential barriers and facilitators to widespread implementation of enhanced appointment reminder messages. We will conduct semi-structured interviews with key informants (10 Veterans locally and 30 VHA staff nationally). Interview guides will be informed by selected domains and constructs from the Consolidated Framework for Implementation Research.

SCIENTIFIC RATIONALE AND SIGNIFICANCE

BACKGROUND

Why are no-shows a critical health services issue now?

[figure not shown]
Providing and maintaining patient access to care has been declared by leadership as the Veterans Health Administration's (VHA) highest priority. Deficits in access have been shown to contribute to decreased patient satisfaction³⁷, higher mortality rates³⁸ and diminished quality of care³⁹. Amidst an environment of limited access and long wait times, VHA is simultaneously struggling with "no-shows."

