effectiveness of interventions varies. For example, we will explore whether the effect of the interventions differ between men and women. To analyze our exploratory outcomes on appointment wait time, we will evaluate time-to-completed appointment using an extended multivariate Cox regression model to account for multiple appointments at the patient level and clustering at the provider level.

Aim 2 Hypotheses: To address Hypothesis 1 (Each intervention group will have a lower no-show rate, as compared with usual care) and Hypothesis 2 (Each intervention group will have a higher cancellation rate, as compared with usual care), we will conduct pairwise comparisons to test for differences between the interventions and usual care as $H_0: \beta_j=0$ for Interventions $j=1,2,3,4$.

Aim 3 Hypothesis (Effect size of nudges will vary by intervention arm such that some categories of nudges have a larger proportional effect than others): We will conduct pairwise comparisons of no-show and cancellation rates by testing the linear combinations between each of the four intervention arms (e.g., Intervention 1 and Intervention 2; $H_0: \beta_1=\beta_2$).

Aim 4: ATLAS.ti software will be used for data management. We will employ a “rapid assessment process,” which is useful for quickly developing understanding from an insider’s perspective and informing future implementation efforts^{81,92}. This multi-step process will be as follows: 1) create domain names for each interview question; 2) create and test a summary template; 3) summarize interview transcripts using the summary template, and 4) transfer summaries into a matrix (respondent x domain) data display⁹³. Our summary template will consist of domains and constructs from our interview guides (i.e., CFIR), and we will compose a templated summary for each interview. We will review these summaries on a regular basis (approximately every five interviews) to ensure interviews build iteratively on emergent findings.

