K. Power Analyses: For our Aim 2 and Aim 3 power calculations, we used FY2016 stop code-level no-show rates at each of the eight locations and the provider-level number of scheduled appointments at each location to conduct Monte Carlo simulations. We assumed two possible differences in no-show and cancellation rates for the interventions (1.9% and 2.7%), which represent changes in appointment attendance on par with our pilot data and two prior RCTs using similar variations in BE messages in appointment reminders³¹. Because baseline no-show rates in the RCTs were lower than ours, leading to possible floor effects, these estimated effects are relatively conservative⁹⁴. We assumed a total of 256 providers randomized to the interventions. In addition, to account for intra-class correlation among providers and the effects of over-dispersion, we allowed for correlated binary measurements to be correlated with parameter $\rho = (\sigma_b^2/\sigma_b^2 + \pi^2/3)$. We varied ρ between two and five percent. All hypothesis tests were two-sided, with no adjustments for multiple comparisons. As the

number of providers, patients and scheduled appointments within providers and no-show rates differ between primary care and mental health, separate Monte Carlo simulations were performed to address power and sample size requirements for the two specialties. Each simulation was run a minimum of 500 times. We calculated power as the proportion of times the stated statistical hypothesis was correctly rejected.

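### Hypothesis 2 predicts more advance cancellations in the Aims, but the analysis section ties its formal test to the overall cancellation rate

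*Combined protocol and SAP*

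**What the plan says.** The Aim 2 hypotheses in the specific aims read: "Each intervention group will have a higher advanced cancellation rate, as compared with usual care".

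Section I (Measures) sets out the quantities. "Our secondary outcome will be cancellation rate, defined as the proportion of scheduled appointments that are marked as canceled". It then adds that "we will also determine the rate amongst the subset of cancellations that are advance cancellations and patient-initiated cancellations", and gives the timing rule: "Advance cancellations, defined here as at least five days before appointment". The reason offered for that rule is that a slot freed early enough can be given to another waiting Veteran. Table 3 lists the cancellation rate, the advance cancellation rate and the patient-initiated cancellation rate on separate lines as secondary outcomes.

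Section J (Data Analysis) first says of the mixed logistic model: "We will use a similar approach to analyze intervention effects on our secondary outcomes, cancellation rates". Under Aim 2 Hypotheses it then gives "Hypothesis 2 (Each intervention group will have a higher cancellation rate, as compared with usual care" and continues: "we will conduct pairwise comparisons to test for differences between the interventions and usual care as" a null of zero for each of the four intervention coefficients. The word advance does not appear there.

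Section K (Power Analyses) speaks of cancellation rates without saying which one. It describes its own tests thus: "All hypothesis tests were two-sided, with no adjustments for multiple comparisons".

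**The concern.** The same numbered hypothesis names one endpoint in the aims and another in the section that tests it. The difference cannot be put down to loose wording alone, because section I defines the two terms separately and Table 3 gives them separate lines.

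What is at stake is what a positive or negative result for Hypothesis 2 would mean. The access benefit that the protocol describes comes from slots released early enough to be refilled. The overall rate also counts late cancellations and cancellations made by the clinic. Patients who cancel earlier instead of later deliver the intended benefit without changing the overall rate. More late or clinic-initiated cancellations raise the overall rate without that benefit.

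There is also room for choice. Three cancellation measures by four arms is 3 × 4 = 12 comparisons with usual care. Section A has the two specialties analysed separately, which makes 12 × 2 = 24. Section J gives no multiplicity adjustment. With the deciding measure stated inconsistently, it could be settled after the results are known.

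**Working it through.** No figure in the documents rests on this point, so there is none to reproduce. The check compares the texts and then works through the definitions.

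**Step 1: the texts side by side.**

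| Place | Endpoint named |
|---|---|
| Specific aims, Aim 2, Hypothesis 2 | Advance cancellation rate |
| Section I and Table 3 | Overall, advance and patient-initiated rates, as separate measures |
| Section J, model paragraph | Cancellation rates, plural, by a similar model |
| Section J, Aim 2 Hypotheses | Cancellation rate, with the formal tests attached |
| Section K | Cancellation rates, not specified further |

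Applying the section I definition to the wording in section J, the formal test of Hypothesis 2 is on all cancellations over scheduled appointments.

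**Step 2: what each measure responds to.** Let S be scheduled appointments, A advance cancellations and L all later ones.

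- Overall rate = (A + L)/S
- Advance rate over scheduled appointments = A/S
- Advance share of cancellations = A/(A + L)

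The documents give no baseline for any of these. For illustration only, assume an overall rate of 20% and an advance rate of 10%, so the late rate is 20 − 10 = 10%. The size of change is 2.7 points, the larger difference considered in section K.

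| Scenario | A/S | L/S | Overall | Advance share |
|---|---|---|---|---|
| Baseline | 10.0% | 10.0% | 20.0% | 10.0/20.0 = 50.0% |
| 2.7 points move from late to advance | 12.7% | 7.3% | 20.0% | 12.7/20.0 = 63.5% |
| 2.7 points more late cancellations | 10.0% | 12.7% | 22.7% | 10.0/22.7 = 44.1% |
| 2.7 points more of each | 12.7% | 12.7% | 25.4% | 12.7/25.4 = 50.0% |
| 2.7 points fewer late cancellations | 10.0% | 7.3% | 17.3% | 10.0/17.3 = 57.8% |

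The second row is the benefit sought, and the overall rate does not move. In the third row the overall rate rises by 2.7 points with no more advance cancellations. Neither result depends on the assumed baselines: moving d from L to A leaves A + L as it was, and adding d to L raises A + L by d.

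**Step 3: the denominator.** The section I phrase about a rate amongst a subset of cancellations can mean A/S or A/(A + L). The last two rows show why this matters. The share stays at 50.0% although advance cancellations rose by 2.7 points, and it rises to 57.8% although they did not rise at all. The share conditions on having cancelled, an event after randomisation. The letters are meant to change that event, since every intervention arm carries instructions for changing or cancelling an appointment (Tables 1 and 2).

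**The case against.** The best reply is that the advance rate has not been forgotten. Table 3 lists it as a secondary outcome in its own right, and the model paragraph of section J covers the cancellation rates in the plural. The singular under Aim 2 Hypotheses may be shorthand. A shift from late to early cancelling would then show in the advance-rate model, and a rise made up of late or clinic cancellations would show as an overall increase without a matching one in the advance or patient-initiated rate. This stands. A reader might infer that the hypothesis in the aims goes untested or that the trial could not see such a shift; the documents do not support that. What the reply leaves open is which of these results decides Hypothesis 2.

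It is also fair to say that the denominator phrase follows directly on a definition over scheduled appointments and may simply carry that denominator over. It is an ambiguity to clear up, not an established third outcome.

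Two further inferences should be resisted:

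- **The pilot.** From its 0.6-point fall in no-shows and 3.8-point rise in attendance, a reader might conclude that overall cancellations fell by 3.8 − 0.6 = 3.2 points. The pilot account gives neither the denominators nor an interval, and nothing on when cancellations were made, so it does not favour one cancellation measure over the other.
- **Power.** A reader might conclude that the advance rate is the better-powered endpoint. That depends on baselines the documents do not give and on how many extra cancellations are early ones. Take mental health with 275 providers, an intraclass correlation of 5%, assumed baselines of 20% overall and 10% advance, and an assumed two-sided 0.05 level. A 2.7-point overall rise then has power of about 0.49. The advance rate has about 0.88 if every extra cancellation is early, but 0.38 if half are and 0.13 if a quarter are.

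**Conclusion.** Wrong as written, and it should be corrected. The aims state Hypothesis 2 for the advance cancellation rate, while the section that tests it names the overall rate. The advance rate is planned for analysis but is not named as the endpoint that decides the hypothesis. As written, a move from late to advance cancelling of any size changes the deciding quantity by 0, and late or clinic-initiated increases count in its favour point for point.

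This rests on the section I definitions being applied to the wording of section J, and on no assumed rate. The wording mismatch is certain. How often the two measures would lead to different conclusions cannot be estimated from these documents. The point concerns a secondary outcome and leaves the primary no-show analysis untouched.

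**What to change.** - In section J, Aim 2 Hypotheses, test Hypothesis 2 on the advance cancellation rate, in agreement with the specific aims and the slot-filling rationale.
- In section I, define that rate as cancellations five or more days ahead of the appointment divided by all scheduled appointments, and replace the phrase that leaves the denominator open.
- Report the overall and patient-initiated cancellation rates on the same denominator as supportive secondary outcomes. The patient-initiated rate stays useful because the five-day rule does not say who cancelled.
- Use one term throughout, and say in section K and under Aim 3 which cancellation rate is meant.
- Make the change before outcome data are seen.

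The cost is a wording change. The data source and the five-day definition are already in the protocol, and no stated figure changes.
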